#### 9.4 Study Design:

Describe study design in one to two sentences (e.g., prospective, use of existing records/data /specimens, observational, cross-sectional, interventional, randomized, placebo-controlled, cohort, etc.). Specify the phase – Phase I, II, III, or IV – for FDA-regulated investigational drug research

This study utilizes a single-blinded, randomized controlled non-inferiority trial design.

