#### 9.6 Benefit to the DoD:

State how this study will impact or be of benefit to the Department of Defense

It is the primary aim of the study to demonstrate that low dose intramuscular ketorolac, 15 mg, is not inferior to high dose intramuscular ketorolac, 60 mg, for the treatment of musculoskeletal pain. In proving the primary aim of the study, it is our hypothesis that the total man hours lost will decrease as a result of better pain management at the time of presentation to the emergency department. Second, by demonstrating that the lower dose is not inferior, this study may help increase patient satisfaction scores within military emergency departments. Lastly, by providing evidence with this single-blind, non-inferior study, it may be inferred that our results will add to the current set of literature which could become a pathway to building a larger multi-center study.

During his tenure, the previous Chief of Staff for the Army, GEN Mark Miley, clearly maintained that readiness is the priority of the U.S. Army. The military medical community is front and center in maintaining the DoDs level of readiness. This study aims to demonstrate that low dose intramuscular ketorolac is not inferior to high dose intramuscular ketorolac. By demonstrating non-inferiority, it is postulated that patients receiving the lower dose of ketorolac may experience a faster return to work period. This shorter period may equate to less man hours lost. This hypothesis is based on previously demonstrated higher incidents of dose related adverse events.

We anticipate that there will be a lower rate of adverse outcomes by utilizing lower doses of ketorolac. These findings result in multiple benefits to the DoD, service member, and beneficiary. First, by showing a lower rate of adverse outcomes, treating with the lower dose may improve readiness by decreasing lost man hours. Secondly, reducing the amount of adverse effects while maintaining the same level of therapy, patient satisfaction may improve, as well.

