    1. Objective adverse events are those identified during reassessment immediately following the initial ketorolac administration, and at the 30 minute and 60 minute re-evaluation intervals. To better facilitate analysis, a list of the most commonly occurring objective adverse events, according to UpToDate.com, will be provided for the investigator to choose from. This list will be included on the Ketorolac Research Form. Objective adverse events are any (1.) subjective events (signs or symptoms) which can be validated or observed by study investigators (such as diaphoresis), (2.) are obvious to the investigator, but perhaps not the patient (mild facial swelling or rash) or (3.) abnormal vital signs. Blood pressure and heart rate measurements will be taken at the 30 minute and 60 minute intervals. Any deviation of blood pressure or heart rate which would meet exclusion criteria for this study would prompt immediate notification of the attending provider and the patient would be excluded from the study.
    2. Subjective adverse events are any symptoms conveyed by the subject, but are not measureable, observable or verifiable by the investigator. To better facilitate analysis, a list of the most commonly occurring subjective adverse events, according to UpToDate.com, will be provided to the study subject to choose from. Examples of subjective adverse events may include dizziness, light headedness or nausea (this is not an exhaustive list of subjective adverse events).
2. Informed Consent Form: this document describes important details and purpose of the research, risks, benefits, alternatives, use of PHI and PII, obtains consent from female potential subjects for a POC UHCG and obtains official consent in the form of the subject's signature. This form will be explained in detail with the patient to ensure their complete and total understanding. The patient will be given as much time as possible to contemplate the decision to enroll as a subject in this study. However, once roomed in the ED, the patient will no longer be eligible to enroll. The patient will be given the opportunity to ask as many questions as possible prior to obtaining signature and will be informed that they have the right to withdraw from the study at any point.

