#### Medication Administration

The primary investigator (PI) will maintain a resident-status through the Army-Baylor Doctor of Science Physician Assistant Studies Program for the entire research period of this study. The PI is a licensed physician assistant-certified and can under normal circumstances prescribe medication without approval by an attending physician. However due to the PI resident-status, all final treatment decisions (to include the ketorolac dosing used for this study) must be approved by a WBAMC ED attending provider.

For purposes of this study, the attending provider is usually a physician, but may be a physician assistant or nurse practitioner, and is the provider responsible for the subject's medical care at the time of data collection. Therefore, the attending provider is not a single individual. The PI may have a different attending provider for each shift or the attending may vary (being more than one individual) within one specific ED shift. Again, the attending provider is the final medical authority for every subject and it is the attending provider who will ultimately approve or disapprove ketorolac dosing regimens as they pertain to this study.

For instance, the PI may enroll and randomize a patient to the 15 mg ketorolac group. The PI will communicate this to the attending provider. However, the attending provider may reject the 15 mg dose and opt for a lower dose, higher dose or no ketorolac dose at all. For this reason, the inclusion and exclusion criteria for this study will document attending provider approval of the dosing regimen to which the patient is randomized prior to administration of the ketorolac.

The Regional Health Command Central (RHC-C) Human Research Protection Program was consulted on this issue specifically. Their guidance was that, for the purposes of this study, the attending physicians are not human subjects research in this study and do not require formal written consent to signify approval of the randomized ketorolac dose. However, they recommended that the PI obtain concurrence with the dose from the attending provider. The investigators for this study will have the attending provider sign the Ketorolac Research Form signifying their concurrence with the randomized dose.

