All appropriate provider and nursing policies, safeguards and regulations governing the preparation and administration of parenteral medication within the WBAMC ED will be followed and standard of care for the injection of ketorolac will not be altered, omitted or deviated from industry, ethical, moral or hospital standards. The investigators will not have any part in preparation or administration of the ketorolac-this will be completely handled by WBAMC ED nursing staff and the order for the ketorolac will have already been approved and prescribed by the WBAMC attending ED provider through the EHR.

As the medication is prepared for administration, the investigator will educate the subject on the use of the VAS and annotate their pre-treatment pain score on the VAS form. For the purposes of this study, the VAS is a validated tool that will be used to objectively measure the subject's response to ketorolac.

The subject will then be injected intramuscularly with the dose of ketorolac randomized to the patient based on the Subject Study Number assigned to the randomized packet, which was assigned to that subject. Again, all appropriate provider and nursing policies, safeguards and regulations governing the preparation and administration of parenteral medication within the WBAMC ED will be followed and standard of care for the injection of ketorolac will not be altered, omitted or deviated from industry, ethical, moral or hospital standards.

Following the administration of ketorolac and at the 30 and 60 minute intervals, VAS scores will be recorded, the patient will be assessed for adverse effects (objective and subjective) and blood pressure and heart rate measurements will be taken. At the conclusion of the 60 minute period and documentation of the VAS and any adverse effects, the data collection phase will be considered complete. The subject will be notified that the study has concluded. The attending provider will then continue with evaluation, treatment, and disposition, as indicated.

As outlined during the consent process, additional analgesia will be available during the course of the study. The decision to provide additional analgesia will be made by the attending provider in consideration of the study subject's clinical scenario. Study subjects who receive additional analgesia will be unenrolled from the study at the time of administration of the additional analgesia.

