**11.5 Please provide a justification for your sample size**

In this study, we assume that we are comparing the mean VAS between the 2 Groups, and the margin of non-inferiority is -13 mm. The actual difference between the means is assumed to be 0 and the standard deviation is assumed to be 27 for the 2 Groups (estimated from the Motov manuscript). Group sample sizes of 55 and 55 achieve 80% power to detect non-inferiority using a one-sided, two-sample equal-variance t-test with alpha of 0.05. The sample size per arm was increased from 55 to 61 to account for an anticipated 10% dropout or withdrawal of subjects (5.5 subjects was rounded to 6 subjects).

**11.6 Data Analysis Plan: Complete description: Background, Objectives, Design, Step by Step how the project is going to be done, Data analysis plan:**

To test for non-inferiority of dose 15mg to dose 60 mg using the VAS pain score, the analysis to be used is called an interval test. The hypothesis will be tested using the construction of one-sided confidence intervals or one-sided, two-sample equal-variance t-test with alpha of 0.05. To test that the lower dose has less adverse effects, we will use the one-sided z-test for testing two independent proportions. All tests will be conducted at the 0.05 level of significance.

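### Investigators who can see the dose judge the objective adverse events, so a finding of fewer events on 15 mg could come from observer bias

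*Protocol*

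**What the plan says.** - **Blinding.** Protocol 9.4: "This study utilizes a single-blinded, randomized controlled non-inferiority trial design". Neither document says who is blinded.
- **Who judges objective events.** In Protocol 10.1 (description of the Ketorolac Research Form, repeated in 10.2), the investigator picks events from a list right after injection and at 30 and 60 minutes. They include signs that "are obvious to the investigator, but perhaps not the patient (mild facial swelling or rash".
- **How the dose is visible.** Under Randomization and Study Subject Packet Creation, the Subject Study Number contains 15 or 60 (the example is K15-30) and is written on the packet and every document in it. Under Medication Administration, in a worked example of a patient randomised to 15 mg, "The PI will communicate this to the attending provider". The attending then signs concurrence with that dose on the Ketorolac Research Form, which is also where adverse events are recorded.
- **Who handles the drug.** The attending prescribes in the EHR and nursing staff prepare and inject. "The investigators will not have any part in preparation or administration of the ketorolac".
- **Subjective events.** Subjects circle these on the form. Under 10.2 the investigators later confer on and categorise them, with no masking stated.
- **Expectation and test.** Protocol 9.6: "We anticipate that there will be a lower rate of adverse outcomes by utilizing lower doses of ketorolac". Protocol 11.6: "To test that the lower dose has less adverse effects, we will use the one-sided z-test", and "All tests will be conducted at the 0.05 level of significance". The SAP instead names Fisher's exact test, worded as looking for a difference, with no sidedness.

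**The concern.** The secondary outcome is the number of subjects with adverse events, objective and subjective together. Part of it rests on discretionary calls by people who can read the arm off the form in front of them and have said which arm they expect to do better. A mild rash noted more readily in a subject known to have had 60 mg becomes an event, and the same finding after 15 mg may not. The later categorisation of subjective events is open to the same influence. The subject also handles forms bearing the same number, so even the subject's blinding depends on not noticing it.

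The claim at stake is that the lower dose is safer, which Protocol 9.6 and 14.4 present as a benefit of the study. The protocol's test looks in exactly the direction in which the bias would push. The plan guards VAS measurement against bias by deferring it until all data are collected (10.2) but gives adverse-event calls no similar protection.

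**Working it through.** **The plan's own figure.** The only calculated sample size is for the primary VAS test (11.5): margin 13 mm, SD 27 mm, true difference 0, one-sided 0.05, 80% power. The normal formula gives n = 2 × (1.645 + 0.842)² × 27² / 13² = 53.3, so 54 per arm. With the noncentral t, power is 0.7998 at 54 and 0.806 at 55, so 55 is reproduced. Then 55 × 1.10 = 60.5, rounded to 61. No calculation is given for adverse events.

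**Inputs for adverse events.** From the documents: 61 per arm (11.4), level 0.05, and a test that differs between protocol and SAP. Assumed: equal true rates p in both arms, from 10% to 40%, and d = 5 or 10 points of extra subjects recorded as having an event on 60 mg. Protocol 14.1 lists general rates (for example headache 17%, nausea 12%), but none by arm or for a 60-minute window. In subjects, 61 × 0.05 ≈ 3 and 61 × 0.10 ≈ 6.

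**Method.** Let X (15 mg) be binomial(61, p) and Y (60 mg) binomial(61, p + d). The chance of a false finding of fewer events on 15 mg is the sum, over all pairs (x, y) for which the test rejects in that direction, of P(X = x) × P(Y = y). The rejection rules are:

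- one-sided z: (y − x)/61 divided by √(2 p̄(1 − p̄)/61) exceeds 1.645, with p̄ = (x + y)/122;
- one-sided Fisher: hypergeometric P(X ≤ x given x + y) ≤ 0.05;
- two-sided Fisher: p ≤ 0.05 with y > x.

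**Results, 61 per arm, true rate 20% in both arms**

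| Test | No bias | 5 points | 10 points |
|---|---|---|---|
| One-sided z (protocol) | 5.1% | 16.6% | 36.4% |
| One-sided Fisher | 3.2% | 11.7% | 28.4% |
| Two-sided Fisher, this direction | 1.4% | 6.4% | 18.6% |

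**Hand check of 16.6%.** p̄ = (0.20 + 0.25)/2 = 0.225. Null SE = √(2 × 0.225 × 0.775/61) = 0.0756. Alternative SE = √((0.20 × 0.80 + 0.25 × 0.75)/61) = 0.0755. (0.05 − 1.645 × 0.0756)/0.0755 = −0.985, and Φ(−0.985) = 0.162, close to the exact value.

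**Range over true rates of 10% to 40%, 61 per arm**

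| Test | No bias | 5 points | 10 points |
|---|---|---|---|
| One-sided z | 5.1–5.3% | 14–21% | 29–47% |
| One-sided Fisher | 2.8–3.6% | 10–15% | 23–38% |
| Two-sided Fisher, this direction | 1.1–1.7% | 6–8% | 16–25% |

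With 55 per arm and a 20% rate, the z-test gives 4.8%, 15.2% and 33.4%.

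**The case against.** **The size of the bias is not in the documents.** The outcome counts subjects with any event, so a biased call matters only in a subject with no other event. Most of the rates listed in Protocol 14.1 are for symptoms that subjects circle themselves, and nothing shows that six extra subjects in an hour is plausible for signs only the investigator sees. This stands: the figures show sensitivity and are not a forecast.

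**The one-sided test is the protocol's only.** This stands too. Under a two-sided Fisher test the absolute error is smaller, but the bias remains: 1.4% becomes 6.4% with three extra subjects.

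**A reader might infer that the person who carries the dose always judges the events.** The protocol names only the PI as relaying the dose, in an example, and other investigators take part. It does not say who assesses each subject. The point does not need it, because any assessor using the forms sees the number.

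**A reader might also infer that the investigator coaches the VAS at 30 and 60 minutes.** The documents do not support this. Teaching takes place once, before injection, with retraining only after an invalid mark (10.1, 10.2). Subjects mark an unnumbered line themselves, and the investigators must agree on each measurement.

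**Some events leave little discretion.** Blood pressure and heart rate are measured, and the exclusion limits are numerical. Those limits trigger notification and removal from the study, however, and the plan does not say whether they also define an event.

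**The visible dose has a purpose.** Protocol 10.1 uses it as a check that the right dose is given, and human-research-protection guidance recommended that the PI obtain the attending's concurrence. Any change must preserve both functions, so it would be wrong to call the bias free to remove.

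**Conclusion.** The point holds as a weakness in the secondary outcome that should be corrected. Objective adverse events are judged, and subjective ones categorised, by investigators who can see the dose and expect fewer events on 15 mg. No masked assessor is described. The documents do not show that bias will occur or how large it would be.

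Under the stated assumptions (20% true rate in both arms, 61 per arm), about three extra subjects recorded on 60 mg raise the false-positive chance from 5% to 17% with the protocol's z-test, from 3% to 12% with one-sided Fisher, and from 1.4% to 6% with two-sided Fisher in that direction. About six extra subjects give 36%, 28% and 19%. No choice of test removes the problem, although the two documents must still be reconciled on which test applies.

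**What to change.** 1. In Protocol 9.4, state that subjects and outcome assessors are blinded.
2. In 10.1, use neutral subject numbers on the packet and all forms.
3. Put each allocation on a sealed card, prepared and held by someone who does not assess outcomes. This needs saying because only investigators have access to the packet locker.
4. Replace the step in which the PI relays the dose: the attending opens the card, signs concurrence on it instead of on the Ketorolac Research Form, and prescribes in the EHR. The recommended concurrence is kept; only its place changes.
5. The nurse prepares and injects as already planned, with the dose kept from the assessing investigator, including during VAS teaching while the drug is drawn up.
6. Keep investigators blind until adverse-event recording, categorisation of subjective events and VAS measurement are final. The attending may disclose the dose for care at any time.
7. Name one adverse-event test and its sidedness, the same in Protocol 11.6 and the SAP.

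Cost: protocol wording and one card per packet. The existing assessor is blinded, so no second assessor is needed and the sample size stays at 122. A holder for the list must be named; the documents give no staffing figures and show total funding of 0 (7.1). The drawbacks are one more item for the attending to handle, and that the check of the randomised dose moves from the investigator to the attending and nurse.

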#### Medication Administration

The primary investigator (PI) will maintain a resident-status through the Army-Baylor Doctor of Science Physician Assistant Studies Program for the entire research period of this study. The PI is a licensed physician assistant-certified and can under normal circumstances prescribe medication without approval by an attending physician. However due to the PI resident-status, all final treatment decisions (to include the ketorolac dosing used for this study) must be approved by a WBAMC ED attending provider.

For purposes of this study, the attending provider is usually a physician, but may be a physician assistant or nurse practitioner, and is the provider responsible for the subject's medical care at the time of data collection. Therefore, the attending provider is not a single individual. The PI may have a different attending provider for each shift or the attending may vary (being more than one individual) within one specific ED shift. Again, the attending provider is the final medical authority for every subject and it is the attending provider who will ultimately approve or disapprove ketorolac dosing regimens as they pertain to this study.

For instance, the PI may enroll and randomize a patient to the 15 mg ketorolac group. The PI will communicate this to the attending provider. However, the attending provider may reject the 15 mg dose and opt for a lower dose, higher dose or no ketorolac dose at all. For this reason, the inclusion and exclusion criteria for this study will document attending provider approval of the dosing regimen to which the patient is randomized prior to administration of the ketorolac.

The Regional Health Command Central (RHC-C) Human Research Protection Program was consulted on this issue specifically. Their guidance was that, for the purposes of this study, the attending physicians are not human subjects research in this study and do not require formal written consent to signify approval of the randomized ketorolac dose. However, they recommended that the PI obtain concurrence with the dose from the attending provider. The investigators for this study will have the attending provider sign the Ketorolac Research Form signifying their concurrence with the randomized dose.

Study participants whose randomized dosing regimens are rejected by the attending provider will be excluded from the study. Again, attending provider concurrence with the randomized ketorolac dosing utilized in this study will be documented on the Ketorolac Research Form and is reviewed in the inclusion and exclusion portion of this application.

Prior to administration of ketorolac, a review of systems (ROS) will be performed with each patient to ensure that the subject has no medical history or other acute medical problems which would meet exclusion criteria for this study. However, this information will not be documented on any forms and will not be accessed through the EHR. The ROS is an anatomic or physiologic systems based detailed

interview with the patient to discuss their overall health and to identify any other medical issues that may or may not be connected with the patient's reason for ED visit.

The ROS used for this study is located within this application and will be located in the appendix of the manuscript when this study is complete. The study investigators' ROS may be separate from the actual attending provider ROS. The attending provider will perform their own ROS based on standard medical history taking. However, the ROS performed by the investigators for the purpose of this study will be used to discover any other medical issue or issues which may meet inclusion or exclusion criteria. If deemed pertinent to patient care, information obtained by performing the investigator ROS will be communicated verbally to the attending provider, so that they are aware that the patient may require evaluation for medical issues beyond an acute MSK injury or pain.

Ketorolac will be prepared for IM injection by the nursing staff assigned to the patient once the following have taken place:

1. Study subject has granted consent
2. Pregnancy is excluded
3. Breast feeding is excluded
4. Inclusion criteria are met
5. None of the exclusion criteria are met
6. The ROS is complete
7. The attending provider agrees to the randomized dose and formally prescribes the randomized dose of ketorolac through the EHR
8. Ketorolac will then be prepared for IM injection by the nursing staff assigned to the patient

All appropriate provider and nursing policies, safeguards and regulations governing the preparation and administration of parenteral medication within the WBAMC ED will be followed and standard of care for the injection of ketorolac will not be altered, omitted or deviated from industry, ethical, moral or hospital standards. The investigators will not have any part in preparation or administration of the ketorolac-this will be completely handled by WBAMC ED nursing staff and the order for the ketorolac will have already been approved and prescribed by the WBAMC attending ED provider through the EHR.

As the medication is prepared for administration, the investigator will educate the subject on the use of the VAS and annotate their pre-treatment pain score on the VAS form. For the purposes of this study, the VAS is a validated tool that will be used to objectively measure the subject's response to ketorolac.

The subject will then be injected intramuscularly with the dose of ketorolac randomized to the patient based on the Subject Study Number assigned to the randomized packet, which was assigned to that subject. Again, all appropriate provider and nursing policies, safeguards and regulations governing the preparation and administration of parenteral medication within the WBAMC ED will be followed and standard of care for the injection of ketorolac will not be altered, omitted or deviated from industry, ethical, moral or hospital standards.

Following the administration of ketorolac and at the 30 and 60 minute intervals, VAS scores will be recorded, the patient will be assessed for adverse effects (objective and subjective) and blood pressure and heart rate measurements will be taken. At the conclusion of the 60 minute period and documentation of the VAS and any adverse effects, the data collection phase will be considered complete. The subject will be notified that the study has concluded. The attending provider will then continue with evaluation, treatment, and disposition, as indicated.

As outlined during the consent process, additional analgesia will be available during the course of the study. The decision to provide additional analgesia will be made by the attending provider in consideration of the study subject's clinical scenario. Study subjects who receive additional analgesia will be unenrolled from the study at the time of administration of the additional analgesia.

